6.2 Screening

Potential subjects will be screened for exclusion criteria. Screening for depression will use the CES-D^{34,35}. The Center for Epidemiological Studies-Depression Scale (CES-D) is 20-item measure rating frequency of depressive symptoms over the past week. Scores of 24 or higher are associated with severe clinical depression and will be excluded.^{34,35} The CES-D and its subscales have been strongly related to physiological variables in previous ovarian cancer research.¹² So that they can receive adequate attention, survivors with scores equal to or above 24 will not be included in groups. Instead, they will be mailed a list of resources that they can use to address their health concerns. If the study team has concerns about a subject's ability to understand English for participation in the intervention, the Wide Range Achievement Test (WRAT)⁵⁶ will be administered. Mental health history and current status and substance use will be abstracted from survivor medical records and will be included in screening questions. This screening will occur at the clinical sites for local survivors, will occur at Fred Hutch/University of Washington Cancer Consortium for survivors recruited from Alaska and Montana, and by Redcap screening interface or by phone at the Coordinating Core for survivors from elsewhere. It should be noted that because of time it may require to fill the various cohorts, time between screening and randomization may vary. It is possible that potential subjects may have recurred or gone on active chemotherapy before the start of the trial. This will be assessed in the initial assessment which is done within 1-2 weeks of the study. In the case of such a change, these individuals will still be allowed to participate in the intervention.

6.2 Randomization

Assignment to either ML or HL will be done by cluster-randomization stratified by time slot as follows. When subjects enroll, they will provide their availability for each of 3 time slots during which a group will be offered. Subjects will be assigned to a time slot for a web group cohort according to their availability, in the order of enrollment, with each cohort comprised of 5-8 subjects. Before randomization subjects will be re-contacted to confirm that they are still available. Once a time-slot cohort of 5-8 is filled, the cohort will be randomized to either ML or HL, drawn from the corresponding stratum. The cluster-randomization for each strata will employ permuted blocks of block size 2 or 4. To avoid a cluster having a majority of participants with recurrence an exception will be made for subjects with recurrence, such that if there are already 3 subjects with recurrence in the same web-group cohort, the subject will be assigned to the next cohort at that time slot. To minimize waiting time, when the first person recruited has been waiting 3 months of longer, the cohort may begin with at least 5 subjects. Randomization lists will be generated by the statistician prior to the enrollment of subjects and allocation will remain concealed until a group of 5-8 needs to be assigned. The randomization sequence will be stored in a password protected file via a password protection software interface. The Research Coordinator will be the only person with access to this file. When a group is complete and ready to start, to facilitate planning, the group will be randomized by the research coordinator accessing the file. Upon entering an ID code for that particular group an assignment will be shown for that group. Facilitators will be informed approximately 1-2 weeks in advance so that they can plan for the group. It should be noted that facilitators' knowledge of group assignment the week before the group starts will not bias subject recruitment because the slots will have already been filled for that group. Subjects

will learn their randomization via a letter sent through mail/email. Randomization should render equal representation of racial/ethnic, SES, and geographic backgrounds, and recurrence status but we will control for any baseline differences.

6.3 Study Activities

The following procedures refer to both arms of the intervention trial. Subjects will be given the option of using their own tablets. laptops, or desktops for the group conferencing, or a studyprovided tablet (and headset if necessary) or webcam which will be mailed out to them if they need it. Tablets with wireless connectivity will be available for subjects who do not have internet connections available. Subjects will return the tablets or webcams when their study participation is completed. Groups will begin when a cohort of 8 subjects has been randomized. Groups may begin with 5-7 individuals if any participants have been waiting for longer than 2 months for their group to start. 2-3 cohorts of each arm of the study will be conducted simultaneously to accommodate different time preferences of subjects. Subjects will receive periodic reminders from the time of their consent to the beginning of their group about the total number of people enrolled in their respective group, and when they can approximately expect group activities to begin. In the unlikely circumstance that following randomization but before participation in Week 0 a participant has circumstances arise that prevent their participating in the group, the participant may be rescheduled to participate in a future group of the same randomized arm. However, if that rescheduling occurs more than a month following their initial completion of baseline surveys, they will be requested to complete their baseline surveys again before their new group starts.

Before beginning either arm of the intervention, subjects will receive a guide with a link to surveys, instructions for use of the website and videoconferencing, and will have individual training phone calls/zooms for using the website and web-interface conferencing with the study team at UI. The first training will take place before randomization, and the second post-randomization. When a cohort time slot has been filled, subjects will complete an initial assessment using a secure REDCap interface housed at UI and subsequently subjects will be randomized. Subjects will receive notification of their randomization via a letter sent through mail or email. They will then participate in a web-based introductory group informational session with members of their group (Mindful Living or Healthy Lifestyles). This gives subjects additional practice using web conferencing in a group setting and introduces the expectations and ground rules for the group. Subsequently, each subject will attend 10 group sessions lasting 1.5 to 2 hours via secure web-video conferencing. Number of log-ins, extent of meditation practice and daily reflections, and session attendance are assessed on the study website or through brief questions sent daily and securely through REDcap.

Subjects will participate for 12 months following randomization. There will be a booster session at approximately 4.5 and at 9-10 months post-randomization. After the 11 week session, research coordinators may contact participants over phone, by email, or by text to remind them of their booster sessions and surveys. There will be an assessment at following completion of the group (at approximately 3-months post-randomization), at 6-months and 12-months post-randomization. Participants will receive \$20 for completing the assessment at 6-months and another \$20 for completing the assessment at 12 months. There will be approximately a 30 day window on either side of these dates to account for potential scheduling issues.

If participants wish to contact other participants at the end of their participation in their respective group, they can do so by using the private chat function of Zoom. They can also contact the study after their groups have finished to share their contact information with other participants. Establishing contact with other participants at the end of a group's sessions is not a requirement

for this study. During their participation, participants will also receive a letter thanking them for their support and a gift tote-bag (Attached: Living Well 10 Week Thank You Letter). After the 11-week session, participants may also, if they wish, submit 5-10 minute testimonial videos or testimonial texts about their experience of the program which can be uploaded to the study website at (livingwellstudy.org) with the participant's permission, or shared on social media (Twitter, Facebook, Reddit, TikTok) with their permission. At successful completion of 12-month surveys, depending on which group participants are randomized to, they will either receive a USB containing recordings or a document containing summary of the information covered in the group they were not randomized to.

Recordings of missed sessions will be made available to people who miss a session. If participants miss a session and choose to view a recording of the missed session, they are not to share the contents of the recording with anyone so that the confidentiality of the other participants can be preserved. However, even if participants arrange a time and watch the recording for a missed session, that session will still count as missed, and they may not be able to continue if they miss more than 2 sessions. In the event that a participants misses a session, the group leader will have the option of calling the participant later in the week to check in and see if the participant has been able to keep up with study items.

Blood Spot Sub-study:

Blood spots will be collected before randomization of the intervention and again within 2 weeks following the end of the 11-week intervention. If subjects consent to this sub-study, they will be provided with two small kits that will contain a lancet to do the finger-prick, an alcohol swab for sterilizing their skin, cotton gauze for cleanup, a band aid, the blood spot collection card, and a pre-paid return envelope for sending the materials back. After subjects who have consented for the substudy receive their bloodspot kits, they can be contacted over the phone and walked through the process if necessary. They will be provided with reference materials on how to use items in the bloodspot kit. Subjects will then return the completed Blood Spot Card in the pre-paid envelope. They will also be contacted at the end of the group intervention and walked through the process a second time should this be considered necessary for their post group finger prick.

TABLE 3. FLOW CHART OF STUDY TIME-POINTS

Procedures	Screening	Enrollment	Pre-Randomization	Randomization ^d	Pre-Group Activities	Week 1	Week 2	Week 3	Week 4	Week 5	Week 6	Week 7	Week 8	Week 9	Week 10	Week 11	Week 12	Week 19-20	Week 26	Week 39-40	Week 52	
Screening	Х																					
Informed consent		Х																				
Demographics		Х																				
Medical history ^a	Х	Х																				
Assessments ^b			Х														Х		Х		Х	
Randomization ^c				Х																		
Technical training			Х		Х																	
Group introduction						Х																
Study intervention							Х	Х	Х	Х	Х	Х	Х	Х	Х	Х						
Booster sessions																		Х		Х		
Adverse event review						x	x	x	x	x	x	x	x	x	x	x	x	x	x	x	x	
& evaluation						^	^	^	^	^	^	^	^	^	^	^	^	^	^	^	^	
a: Disease and treatment status b: FACT-O, PSS, AAQ-II, BEAQ, FACIT-F, MOCS, CESD, POMS-SF, FMI, CWS, Brief COPE, SPS, PSQI, Godin, PHQ, demographics, COVID survey c: See section 6.0 for randomization process d. technical training and pre-group assessments may occur before or after randomization																						

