5.1. Primary Outcomes (Endpoints)

Health Related Quality of Life: The Functional Assessment of Cancer Therapy-Ovarian (FACT-O) includes 4 subscales related to dimensions of HRQOL, including physical, functional, social, and emotional well-being and a 12-item ovarian cancer-specific subscale related to ovarian cancer and treatment-specific HRQOL issues.^{28,29}

Current Stress: The Perceived Stress Scale³⁰ contains 14-items assessing feeling in control vs. overwhelmed with current stressors over the last month. Internal reliability and construct validity are high³¹ and scores have previously been associated with illness markers.^{12,32,33}

Depressive Symptoms: The Center for Epidemiological Studies-Depression Scale (CES-D) is 20item measure rating frequency of depressive symptoms over the past week. Scores of 24 or higher are associated with severe clinical depression.^{34,35} The CES-D and its subscales have been strongly related to physiological variables in previous ovarian cancer research.¹²

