AAQ	2.8	2.5	0.284	2.3 (0.65)	2.5 (0.71)	-2.7 (-0.76)	(-6.3, 1.0)

Table 6. Power Considerations

7.1. Statistical analyses for Aim 1

Aim 1 will be tested using linear mixed model (LMM) analyses for repeated measures with treatment group (ML vs. HL), time, and treatment*time interaction as fixed effects. Random effects include web group cohort (within treatment) and subjects (within cohort, within treatment). In fitting the LMM, appropriate covariance structures for the longitudinal measures within subject will be considered, such as compound symmetry, or heterogeneous compound symmetry, and then selected based on Akaike Information Criteria (AIC) and Schwarz's Bayesian Information Criteria (BIC). Specifically, to test for immediate change (post-intervention), the linear mixed model analysis will include the baseline and immediate post-intervention timepoints. The difference in immediate change post-treatment between the different conditions will be tested by the interaction effect. For the mixed model analysis of long-term change, data from all 4 timepoints will be used in fitting the model, with the difference in long-term change at 6 and 12 months assessed using tests of mean contrast. Bonferroni adjustment will be applied to the p-value to test for long-term change at 6 and 12 months. For each of the two analyses, if confounding variables are found to differ between the treatment groups such that covariate adjustment is necessary, a secondary comparison of the primary outcome variable between treatment groups will be made by expanding the LMM to include covariates. These variables may include age, education, income, race/ethnicity, geographic location, recurrence, maintenance chemotherapy, recurrence during the study period, and disease stage. Statistical significance for efficacy of ML vs. HL will be based on a two-tailed test at the 0.05 significance level with treatment effect summarized as mean difference with 95% confidence interval. Similar analyses will be performed for the secondary outcome measures.

7.2. Statistical analyses for Aim 2

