8.1 Collection and Storage of Data

REDCap data management software will be used to organize all data including documentation of informed consent, self-report measures, and clinical data. REDCap is supported at UI by NIH CTSA awards. All study information including PHI will be collected in a secure RedCap interface housed at the UI. Self-report measures will be collected after study enrollment. Subjects will be provided with a computer link and instructions for completion of surveys from home during the

week prior to the beginning of the group. Clinical data will be extracted from the medical record by study team members. Intervention website usage will be extracted from the administrator page by study team members.

There may be situations in which subjects would prefer to complete surveys using hard copies. In this situation, hard copy data will be hand entered into RedCap by study team members. When entering subject data, research assistants are only aware of the individual's subject number for the study. All materials are labeled with subject ID and not labeled with any other identifying information (medical record number or name). RedCap data identified only by subject ID may be downloaded into SPSS files kept on password protected servers in the Department of Psychological and Brain Sciences. These password protected files are only available to team members who have set up access through Information Technology Systems ([name]). Electronic data is stored only on these servers. The exception is that data which is being statistically analyzed by the PI or project statisticians is on password protected computers.

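### Table 3 footnote d allows the baseline survey after randomization, and nothing makes the allocation letter wait for it (minor)

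*Combined protocol and SAP*

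**What the plan says.** Section 6.3 gives the order once a cohort time slot is filled: "subjects will complete an initial assessment using a secure REDCap interface housed at UI and subsequently subjects will be randomized". It then says: "Subjects will receive notification of their randomization via a letter sent through mail or email". The Table 3 grid agrees. It marks the first round of assessments only in the Pre-Randomization column, and footnote b lists FACT-O, PSS and CES-D in that battery.

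Footnote d, attached to the Randomization column, says otherwise: "technical training and pre-group assessments may occur before or after randomization". Section 8.1 has women complete the surveys at home in the "week prior to the beginning of the group" and does not restate the order.

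Section 6.3 also covers women who are rescheduled to a later group of the same arm after randomization. If this happens "more than a month following their initial completion of baseline surveys, they will be requested to complete their baseline surveys again".

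Section 7.1 treats baseline as an outcome timepoint: "The difference in immediate change post-treatment between the different conditions will be tested by the interaction effect". Sections 7, 7.1 and 7.4 do not say which survey is the baseline when there are two.

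CES-D is a primary outcome in sections 3, 5.1 and 7.2. The Aim 1 paragraph that opens the power discussion in section 7 lists depressive mood as secondary. All three measures are carried here; the CES-D label needs its own reconciliation.

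**The concern.** The three measures are self-reports, and women are told their arm. A woman who answers the baseline after learning that she is in Mindful Living may answer differently from one who has learned that she is in Healthy Lifestyles. Because the test is the treatment-by-time interaction, a differential shift at baseline passes straight into the estimated difference in change. The same baseline also enters the 6- and 12-month contrasts.

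The order in section 6.3, if followed, prevents this. Footnote d removes that protection without replacing it, since it does not say that the letter must still follow the survey. The plan also does not ask for survey dates to be compared with letter dates, so a report written to the plan would not show whether any baselines were affected.

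**Working it through.** **Side by side.**

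- Section 6.3 text: assessment, then randomization, then letter.
- Table 3 grid: assessment under Pre-Randomization only.
- Table 3 footnote d: assessment on either side of randomization; silent on the letter.
- Section 6.2 (Randomization): facilitators learn the assignment about 1 to 2 weeks ahead, so the cohort is randomized by then. Women learn theirs by letter, with no date given.
- Section 8.1: surveys in the last week before the group.

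Read together, sections 6.2 and 8.1 make a survey after randomization realistic. Whether it also falls after the letter cannot be determined from the documents.

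**The plan's own figure.** Inputs are from section 7 and Table 6: 96 per arm, 6 per cohort, two-sided 0.05, power 0.80. Take SD of change = residual SD × √2, design effect = 1 + (6 − 1) × ICC, and detectable difference = 2.8016 × SD × √(2 × design effect / 96).

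- FACT-Total: SD = 9.3 × √2 = 13.15; design effect 1.05; difference 5.45 (stated 5.5).
- PSS: SD = 4.2 × √2 = 5.94; design effect 1.05; difference 2.46 (stated 2.5).
- CES-D: SD = 5.3 × √2 = 7.50; design effect 1.75; difference 4.01 (stated 4.1).

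The figures reproduce closely, so standard errors can be taken from the stated differences divided by 2.8016: 1.963, 0.892 and 1.463.

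**Size of a possible bias.** Let f be the share of women who answer after disclosure, and d the differential shift between arms in units of the SD of change. Both are assumptions. Then:

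- bias = f × d × SD
- q = bias / SE
- type I error = P(|Z + q| > 1.96)
- power, if the bias runs against Mindful Living = P(Z > 1.96 − (2.80 − q))

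Example, FACT-Total with f = 25% and d = 0.2: bias = 0.25 × 0.2 × 13.15 = 0.66 points; q = 0.66 / 1.963 = 0.335; type I error 0.0630; power 0.694.

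Ranges below run across the three measures.

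| d | f | FACT-Total bias (points) | Type I error | Power if bias is against Mindful Living |
|---|---|---|---|---|
| 0.1 | 10% | 0.13 | 0.0503–0.0505 | 0.781–0.785 |
| 0.1 | 25% | 0.33 | 0.0519–0.0532 | 0.750–0.762 |
| 0.2 | 10% | 0.26 | 0.0512–0.0521 | 0.760–0.770 |
| 0.2 | 25% | 0.66 | 0.0575–0.0630 | 0.694–0.721 |

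The FACT-Total bias is therefore 2% to 12% of the 5.5-point detectable difference.

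**Threshold.** Type I error reaches 0.06 when f × d is 0.0440 (FACT-Total), 0.0443 (PSS) or 0.0575 (CES-D). At d = 0.2 this needs 22%, 22% or 29% of women disclosed first; at d = 0.1, 44%, 44% or 57%.

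**A few women only.** With 6 of 192 (3%) and d = 0.2, the FACT-Total bias is 0.031 × 0.2 × 13.15 = 0.08 points and type I error is 0.0502.

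**The case against.** The intended order is stated in the text and again in the grid; against them stands one footnote, which says nothing about disclosure and does not name the instruments. Being randomized is not the same as knowing the arm. If letters still followed the surveys, using footnote d did no harm of this kind. All of that stands. The link from the footnote to FACT-O, PSS and CES-D runs through footnote b, but that battery is the only assessment the grid marks before the group, so it is the natural reading.

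Two features of the design make a large shift less likely. Section 3 describes the comparator as attention-matched. The PSS is described as "assessing feeling in control vs. overwhelmed with current stressors over the last month", so a letter a few days old touches only part of its recall period.

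A reader might infer that baselines were in fact contaminated, or that the error rate is badly inflated. The documents support neither. With every woman disclosed first and a 0.2 SD differential shift, FACT-Total type I error would be about 0.27, but that would mean the section 6.3 order was never followed, and nothing suggests so. Nor is it right that the matter can never be checked: section 6.5 says that REDCap keeps audit trails, so online survey dates should be recoverable. The plan simply does not ask for the comparison.

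On repeat surveys, section 6.3 calls the circumstance unlikely, and the evident purpose is to replace a stale baseline. Choosing between an older survey from before disclosure and a fresher one after allocation is a real trade-off. Only the request to name the choice in advance stands.

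**Conclusion.** The conflict is real and lies in operative text: footnote d permits what section 6.3 and the grid rule out, and no section ties the letter to a completed baseline. The consequence is a possible bias of unknown direction in the treatment-by-time tests. It arises only from women who answered after disclosure, and only if their answers shift differently by arm.

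Under the assumed shares (10–25%) and shifts (0.1–0.2 SD of change), type I error is 0.050 to 0.063. If few women are affected the effect is negligible. Share, shift and direction are all assumptions. This is a minor point, worth acting on because the remedy is cheap. The undefined analysis baseline for re-surveyed women is a smaller clarification and does not carry the point.

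**What to change.** - **Wording.** Reconcile footnote d and section 8.1 with section 6.3 by stating that a woman's allocation letter is sent only after her baseline survey is complete or closed. A survey after randomization but before disclosure is acceptable, so the footnote's flexibility need not be removed and a late responder need not hold up randomization of a filled cohort.
- **Date check for data already collected.** Compare survey completion dates with letter dates and report, by arm, the share completed after disclosure. For paper surveys use the date on the form where there is one, because "hard copy data will be hand entered into RedCap by study team members" and the entry time may be later.
- **Sensitivity analysis, if any such baselines exist.** Pre-specify one refit of the section 7.1 model with post-disclosure baselines set to missing and nothing else changed. If a model with a common baseline mean across arms is also wanted, run it on the full data too, so that the two changes can be told apart.
- **Repeat surveys.** Before the outcome analysis, state which survey is the analysis baseline for rescheduled women, and show the result with the other.

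The cost is slight scheduling discipline per cohort and a small loss of precision, in the sensitivity analysis only. Sample size and primary power do not change. If enrollment has closed, only the date check, the sensitivity analysis and the repeat-survey clarification apply.
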